4.3. Protocol Deviations

Subjects who did not meet the eligibility criteria for study entry but enrolled in the study will be summarized. The summary will present the number and percentage of subjects who did not meet at least 1 eligibility criterion and the number of subjects who did not meet specific criteria by treatment group based on the All Enrolled Analysis Set. A by-subject listing will be provided for those subjects who did not meet at least 1 eligibility (inclusion or exclusion) criterion. The listing will present the eligibility criterion (or criteria if more than 1 deviation) that subjects did not meet and related comments, if collected.

Protocol deviations occurring after subjects entered the study are documented during routine monitoring. The number and percentage of subjects with important protocol deviations by deviation category (e.g., eligibility criteria, informed consent) will be summarized by treatment group for the All Enrolled Analysis Set. A by-subject listing will be provided for those subjects with important protocol deviation.

4.4. Assessment of COVID-19 Impact

This study was ongoing during the novel coronavirus (2019 nCoV [COVID-19]) pandemic which has caused a disruption in the regular visit schedules for this study. Some subjects were unable to attend onsite visits due to shelter in place guidelines, site closures, or other reasons. This section provides how to handle special situations due to COVID-19 in the analysis.

Adverse events due to COVID-19 will be included in AE analyses if applicable.

4.4.1. Study Drug or Study Discontinuation Due to COVID-19

A by-subject listing of reasons for premature study drug or study discontinuation due to COVID-19 will be created.

4.4.2. Protocol Deviations Due to COVID-19

Similar summary as described in protocol deviations section will be performed for important protocol deviations due to COVID-19.

A by-subject listing will be provided for subjects with important protocol deviation related to COVID-19. A separate listing will be provided for subjects with non-important protocol deviation related to COVID-19.

4.4.3. Missed and Virtual Visits due to COVID-19

A by-subject listing of subjects with missed or virtual visits due to COVID-19 will be provided by unique subject ID number in ascending order .

Information regarding missed or virtual visits due to COVID-19 was collected as free text in the CRF comment fields. The determination of missing or virtual visits due to COVID-19 was done using Natural Language Processing (NLP) to search the CRF comment fields. A detailed explanation of the algorithm is given in [Appendix 2](#).

5. BASELINE CHARACTERISTICS

5.1. Demographics

Subject demographic variables (ie, age, sex, race, and ethnicity) and baseline characteristics (body weight [in kg], height [in cm], body mass index [BMI; in kg/m²]) will be summarized by HCV genotype and total for each treatment group. Age, body weight, and height will be summarized by descriptive statistics (n, mean, SD, median, Q1, Q3, minimum, and maximum). Age categories (< 65 years, ≥ 65 years), sex, race, and ethnicity will be summarized by the numbers and percentages of subjects. Age will be calculated in years at the date of the first dose of study drug. If a subject did not receive study drug after enrollment, the subject's age will be calculated from the date that the subject signed the informed consent form. The summary of demographic data will be provided for the Safety Analysis Set.

A by-subject demographic listing, which includes first dose date, will be provided by unique subject ID number in ascending order.

5.2. Other Baseline Characteristics

Other baseline characteristics include:

- cirrhosis (presence, absence)
- IL28B (CC, non-CC; with non-CC further broken down to CT, TT)
- baseline HCV RNA as a continuous variable and as categories (< 800,000 IU/mL, ≥800,000 IU/mL)
- baseline ALT (U/L) as a continuous variable and as categories ($\leq 1.5 \times \text{ULN}$, $> 1.5 \times \text{ULN}$)
- prior HCV treatment experience (SOF/VEL 12 Weeks: treatment naive, treatment experienced; SOF/VEL/VOX 12 Weeks: treatment experienced)
- prior HCV treatment for treatment experienced subjects (Cohort 1: direct acting antiviral [DAA] + pegylated interferon [Peg-IFN] + ribavirin [RBV], Peg-IFN + RBV, Other[s]; Cohort 2: NS5A +/- DAA[s] and Other[s]; with NS5A +/- DAA[s] further broken down to NS5A + NS5B, NS5A + NS3 +/- NS5B, and NS5A +/- Other[s])
- prior HCV treatment response (non-responder, relapse/breakthrough, early treatment discontinuation, met a virologic stopping rule not otherwise listed, and unknown) for treatment experienced subjects
- estimated glomerular filtration rate (eGFR) using the Cockcroft-Gault equation as a continuous variable and as categories (< 90 mL/min, ≥ 90 mL/min)
- $\text{eGFR}_{\text{CG}} (\text{mL}/\text{min}) = \frac{[(140 - \text{age (yrs)}) \times \text{weight (kg)} \times (0.85 \text{ if female})]}{(\text{serum creatinine (mg/dL)} \times 72)}$, where weight is total body mass in kilograms.

These baseline characteristics will be summarized by HCV genotype and total for each treatment group. Continuous variables will be summarized using descriptive statistics (n, mean, SD, median, Q1, Q3, minimum, and maximum) and categorical variables using the numbers and percentages of subjects. The summary of baseline characteristics will be provided for the Safety Analysis Set.

A by-subject listing of other baseline characteristics will be provided by unique subject ID number in ascending order. The type of assay used to determine the HCV genotype will also be displayed in this listing.

A separate by-subject data listing for cirrhosis determination will be provided for all subjects at screening.

A separate by-subject data listing for prior HCV treatment and response will be provided for all treatment experienced subjects. The listing will display the prior HCV regimen(s) and treatment(s) including the treatment duration, and the prior HCV treatment response.

5.3. Medical History

General medical history data will be collected at screening and a by-subject listing will be provided for Safety Analysis Set.

6. EFFICACY ANALYSES

6.1. Primary Efficacy Endpoint

6.1.1. Definition of the Primary Efficacy Endpoint

The primary efficacy endpoint is SVR12 defined as HCV RNA < LLOQ 12 weeks after discontinuation of study drug in the FAS population. The COBAS® AmpliPrep/COBAS® TaqMan® HCV Quantitative Test, v2.0 will be used to measure HCV RNA. The LLOQ for this assay is 15 IU/mL.

6.1.2. Primary Analysis of the Primary Efficacy Endpoint

For each treatment group, the point estimate of SVR12 and the 2-sided 95% exact CI based on the Clopper-Pearson method {Clopper 1934} will be provided by HCV genotype and overall.

6.1.3. Subgroup Analysis of the Primary Efficacy Endpoint

For each treatment group, the point estimates and the 2-sided 95% exact CIs based on the Clopper-Pearson method will be provided for the SVR12 rates by HCV genotype and overall for each subgroup outlined in Section 3.3.

A forest plot will graphically present the point estimates and the 2-sided 95% exact CIs of the SVR12 rates by HCV genotype for each of the subgroups outlined in Section 3.3. for each treatment group.

6.2. Secondary Efficacy Endpoints

6.2.1. Definition of Secondary Efficacy Endpoints

Secondary efficacy endpoints include the following:

- The proportion of subjects with SVR4 (HCV RNA < LLOQ 4 weeks after discontinuation of study treatment)
- The proportion of subjects with HCV RNA < LLOQ by visit while on treatment
- HCV RNA (\log_{10} IU/mL) change from baseline by visit through the end of treatment (EOT)
- The proportion of subjects with ALT normalization (defined as ALT > ULN at baseline and ALT ≤ ULN at each visit), presented by study visit.

- The percentage of subjects with virologic failure as the following:

On-treatment virologic failure

- HCV RNA \geq LLOQ after having previously had HCV RNA $<$ LLOQ, while on treatment, confirmed with 2 consecutive values (note, second confirmation value can be posttreatment), or last available on-treatment measurement with no subsequent follow up values (ie, breakthrough)
- $> 1 \log_{10}$ IU/mL increase in HCV RNA from nadir while on treatment, confirmed with 2 consecutive values (note, second confirmation value can be posttreatment), or last available on-treatment measurement with no subsequent follow up values (ie, rebound)
- HCV RNA persistently \geq LLOQ through 8 weeks of treatment (ie, nonresponse)

Relapse

- HCV RNA \geq LLOQ during the posttreatment period having achieved HCV RNA $<$ LLOQ at EOT, confirmed with 2 consecutive values or last available posttreatment measurement

6.2.2. Analysis Methods for Secondary Efficacy Endpoints

For analyses of HCV RNA $<$ LLOQ by visit while on treatment and during the posttreatment (SVR) follow-up period, subjects will be assigned a value at each visit based on the analysis visit windows specified in Section 3.7.2. Missing values will be imputed based on the categorical imputation rules described in Section 3.5.1. For each treatment group, the 2-sided 95% exact CI based on Clopper-Pearson method will be provided for the percentage of subjects with HCV RNA $<$ LLOQ at each visit by HCV genotype and total. The overall category for “HCV RNA $<$ LLOQ” will be split into the following 2 subcategories: “ $<$ LLOQ TND” for subjects with target not detected and “ $<$ LLOQ detected” for subjects with $<$ LLOQ in tabular displays.

Graphs for the percentage of subjects with HCV RNA $<$ LLOQ over time during treatment will be displayed by HCV genotype and total for each treatment group.

Summary statistics will be presented for absolute values and change from baseline in HCV RNA (\log_{10} IU/mL), by HCV genotype and total and by visit through EOT for each treatment group. Imputation rules described in Section 3.5.1 will be used to assign HCV RNA values for missing values at a visit that are bracketed by “ $<$ LLOQ TND” and/or “ $<$ LLOQ detected”. Otherwise, a missing excluded analysis will be performed. Plots of the mean \pm SD and median (Q1, Q3) of absolute values and changes from baseline in HCV RNA through EOT will be presented by HCV genotype and total for each treatment group.

For the SVR12 endpoint analysis, a summary table of the number and percentage of subjects with SVR12, virologic failure, and other will be created. This summary will be presented by HCV genotype and overall for each treatment group. All subjects who achieve SVR12 will be categorized as SVR12. Virologic failure will be descriptively summarized as “on-treatment virologic failure” and relapse (which will be broken down by study drug completed yes/no). Subjects who do not achieve SVR12 and do not meet criteria for virologic failure will be categorized as “Other.” The denominator for relapse will be the number of subjects who had HCV RNA < LLOQ on their last observed on-treatment HCV RNA measurement; otherwise, the denominator will be the number of subjects in the FAS. Virologic outcomes will also be provided by cirrhosis status and prior HCV treatment experience on FAS by HCV genotype and overall for each treatment group.

A table for ALT normalization by visit will use similar methodology to the analyses of HCV RNA <LLOQ, but will use a missing excluded analysis. Only those subjects with ALT greater than the ULN range at baseline (defined as the last ALT value collected prior to first dose of study drug) will be included in the analysis of ALT normalization. The summary will be performed by HCV genotype and overall for each treatment group.

Drug resistant substitutions will be analyzed as part of the Virology Study Report.

6.3. Changes From Protocol-Specified Efficacy Analyses

The definition of FAS will be modified to “all enrolled subjects who took at least 1 dose of study drug and had detectable HCV RNA at baseline” to exclude any subject with undetectable HCV RNA at baseline from efficacy analyses.

7. SAFETY ANALYSES

7.1. Adverse Events and Deaths

7.1.1. Adverse Event Dictionary

Clinical and laboratory adverse events (AEs) will be coded using the current version of MedDRA. System organ class (SOC), high-level group term (HLGT), high-level term (HLT), preferred term (PT), and lower-level term (LLT) will be provided in the AE dataset.

7.1.2. Adverse Event Severity

Adverse events are graded by the investigator as Grade 1, 2, 3, or 4 according to toxicity criteria specified in the protocol. The severity grade of events for which the investigator did not record severity will be categorized as “missing” for tabular summaries and data listings, and the most severe will be considered (for sorting purpose only) in data presentation.

7.1.3. Relationship of Adverse Events to Study Drug

Related AEs are those for which the investigator selected “Related” on the AE CRF to the question of “Related to Study Treatment.” Relatedness will always default to the investigator’s choice, not that of the medical monitor. Events for which the investigator did not record relationship to study drug will be considered related to study drug for summary purposes. However, by-subject data listings will show the relationship as missing.

7.1.4. Serious Adverse Events

Serious adverse events (SAEs) will be identified and captured as SAEs if the AEs met the definitions of SAEs that were specified in the study protocol. SAEs captured and stored in the clinical database will be reconciled with the SAE database from the Gilead Pharmacovigilance and Epidemiology Department before data finalization.

7.1.5. Treatment-Emergent Adverse Events

7.1.5.1. Definition of Treatment-Emergent Adverse Events

Treatment-emergent adverse events (TEAEs) are defined as one or both of the following:

- Any AEs with an onset date on or after the study drug start date and no later than 30 days after permanent discontinuation of study drug
- Any AEs leading to premature discontinuation of study drug.

7.1.5.2. Incomplete Dates

If the onset date of the AE is incomplete and the AE stop date is not prior to the first dosing date of study drug, then the month and year (or year alone if month is not recorded) of onset determine whether an AE is treatment emergent. The event is considered treatment emergent if both of the following 2 criteria are met:

- The AE onset is the same as or after the month and year (or year) of the first dosing date of study drug, and
- The AE onset date is the same as or before the month and year (or year) of the date corresponding to 30 days after the date of the last dose of study drug

An AE with completely missing onset and stop dates, or with the onset date missing and a stop date later than the first dosing date of study drug, will be considered to be treatment emergent.

7.1.6. Summaries of Adverse Events and Deaths

A brief high-level summary of TEAEs will be provided for each treatment group by the number and percentage of subjects who had the following: any AE, any AE of Grade 3 or above, any AE of Grade 2 or above, any treatment-related AE, any treatment-related AE of Grade 3 or above, any treatment-related AE of Grade 2 or above, any SAE, any treatment-related SAE, and any AE that led to premature discontinuation of study drug, and any AE that led to interruption of study drug. All deaths (including those that are treatment emergent and those that are not treatment emergent) observed during the study will also be summarized and included in this table.

Adverse event summaries will provide the number and percentage of subjects with TEAEs by SOC and PT for each treatment group based on the safety analysis set as follows:

- All AEs
- AEs of Grade 3 or above
- AEs of Grade 2 or above
- All treatment-related AEs
- Treatment-related AEs of Grade 3 or above
- Treatment-related AEs of Grade 2 or above
- All SAEs (including death)
- All treatment-related SAEs
- AEs leading to premature discontinuation of study drug
- AEs leading to interruption of study drug

Multiple events will be counted once only per subject in each summary. Adverse events will be summarized and listed in alphabetic order of SOC and then by PT in order of descending incidence within each SOC. In summaries by severity grade, the most severe grade will be used for those AEs that occurred more than once in an individual subject during the study.

In addition to the above summary tables, TEAEs will also be summarized by PT only for each treatment group, in order of descending incidence for:

- All AEs
- AEs of Grade 3 or above
- All treatment-related AEs
- All SAEs
- AEs leading to premature discontinuation of study drug
- AEs leading to interruption of study drug

All deaths (including those that are treatment emergent and those that are not treatment emergent) observed during the study will also be summarized.

In addition to the summaries described above, data listings with a variable indicating whether the event is treatment emergent will be provided for the following:

- All AEs
- AEs of Grade 3 or above
- SAEs
- Deaths
- AEs leading to premature discontinuation of study drug
- AEs leading to interruption of study drug

7.2. Laboratory Evaluations

Laboratory data collected during the study will be analyzed and summarized using both quantitative and qualitative methods. Summaries of laboratory data will be provided for the Safety Analysis Set and will include data collected up to the last dose of study drug plus 30 days for subjects who have permanently discontinued study drug. The analysis will be based on values reported in conventional units. When values are below the LOQ, they will be listed as such, and the closest imputed value will be used for the purpose of calculating summary statistics as specified in Section 3.6. Hemolyzed test results will not be included in the analysis, but they will be listed in by-subject laboratory listings.

A by-subject listing for laboratory test results will be provided by unique subject ID number and visit in chronological order for hematology, serum chemistry, and urinalysis separately. Values falling outside of the relevant reference range and/or having a severity grade of 1 or higher on the Gilead Grading Scale for Severity of Adverse Events and Laboratory Abnormalities will be flagged in the data listings, as appropriate.

No formal statistical testing is planned.

7.2.1. Summaries of Numeric Laboratory Results

Descriptive statistics (n, mean, SD, median, Q1, Q3, minimum, and maximum) will be provided by treatment group for ALT, aspartate aminotransferase (AST), albumin, total bilirubin, alkaline phosphatase, uric acid, white blood cell (WBC) counts, neutrophils, lymphocytes, hemoglobin, platelets, reticulocytes, and international normalized ratio (INR), creatinine, and creatinine kinase as follows:

- Baseline values
- Values at each postbaseline visit
- Change from baseline at each postbaseline visit

A baseline laboratory value will be defined as the last measurement obtained on or prior to the date/time of first dose of study drug. Change from baseline to a postbaseline visit will be defined as the visit value minus the baseline value. The mean, median, Q1, Q3, minimum, and maximum values will be displayed to the reported number of digits; SD values will be displayed to the reported number of digits plus 1.

Median (Q1, Q3) of the observed values for ALT, AST, albumin, total bilirubin, alkaline phosphatase, WBC, neutrophils, lymphocytes, hemoglobin, platelets, and reticulocytes will be plotted using a line plot by treatment group and visit.

In the case of multiple values in an analysis window, data will be selected for analysis as described in Section 3.7.3.

The number of subjects with hemoglobin < 10 g/dL or < 8.5 g/dL at any postbaseline visits (up to 30 days after the last dose of any study drug) will be summarized by treatment group.

7.2.2. Graded Laboratory Values

The Gilead Grading Scale for Severity of Adverse Events and Laboratory Abnormalities will be used to assign toxicity grades (0 to 4) to laboratory results for analysis. Grade 0 includes all values that do not meet the criteria for an abnormality of at least Grade 1. For laboratory tests with criteria for both increased and decreased levels, analyses for each direction (ie, increased, decreased) will be presented separately.

7.2.2.1. Treatment-Emergent Laboratory Abnormalities

Treatment-emergent laboratory abnormalities are defined as values that increase at least 1 toxicity grade from baseline at any postbaseline time point, up to and including the date of last dose of study drug plus 30 days for subjects who permanently discontinued study drug, or all available data in the database snapshot for subjects still on treatment at the time of the interim analysis. If the relevant baseline laboratory value is missing, then any abnormality of at least Grade 1 will be considered treatment emergent.

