3.3.1. Toxicity Based Stopping Criteria

The Medical Monitor must be consulted prior to study drug discontinuation of SOF/VEL FDC or SOF/VEL/VOX FDC unless the investigator believes that immediate action is warranted to ensure the continued safety of the subject.

Due to a clinical or laboratory event, administration of study drug may be discontinued. There is no option for SOF/VEL FDC or SOF/VEL/VOX FDC dose reduction. If either SOF/VEL FDC or SOF/VEL/VOX FDC is stopped due to toxicity, it must not be restarted. In these cases that study drug is discontinued permanently, the subject must complete an ET visit. Posttreatment Week 4 and Week 12 visits must also be scheduled, 4 and 12 weeks from the last dose of study drug.

Subjects who meet any of the following laboratory criteria must stop all study drug:

- Elevation of ALT and/or AST above the upper limit of normal (ULN) and $> 5x$ Day 1 or nadir, confirmed by immediate repeat testing
- Abnormal elevation of ALT $> 3 x$ Day 1 and total bilirubin $> 2 x$ ULN, confirmed by immediate repeat testing
- Elevation of ALT $> 15 x$ ULN, confirmed by immediate repeat testing
- Any Grade 3 or greater rash associated with constitutional symptoms
- Any Grade 4 adverse event or laboratory abnormality assessed (and confirmed by immediate repeat testing) as related to SOF/VEL FDC and SOF/VEL/VOX FDC

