- 9) Women who wish to become pregnant or males with female partners who wish to become pregnant during study treatment and through 30 days after the last dose SOF/VEL FDC or SOF/VEL/VOX FDC
- 10) Subjects with any of the following laboratory parameters at screening:
 - a) ALT >10 x upper limit of normal (ULN)
 - b) AST > 10 x ULN
 - c) Direct bilirubin $> 1.5 \times$ ULN
 - d) Platelets $< 50,000/\mu\text{L}$
 - e) HbA1c $> 8.5\%$
 - f) Hemoglobin < 10 g/dL
 - g) Albumin < 3 g/dL
 - h) International Normalized Ratio of prothrombin time (INR) $> 1.5 \times$ ULN unless subject has known hemophilia or is stable on an anticoagulant regimen affecting INR
 - i) Neutrophil count $< 500/\mu\text{L}$
- 11) Use of any prohibited concomitant medications as described in Section 5.4
- 12) Chronic use of systemically administered immunosuppressive agents (eg, prednisone equivalent of > 10 mg/day)
- 13) Known hypersensitivity or contraindication to sofosbuvir, velpatasvir, voxilaprevir or the metabolites or formulation excipients

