8.5.3. Laboratory Evaluations

Selected laboratory data will be summarized (n, mean, SD, median, Q1, Q3, minimum, and maximum) by cohort and study visit along with the corresponding change from baseline.

Graded laboratory abnormalities will be defined using the laboratory toxicity grading scheme in [Appendix 3](#). The incidence of treatment-emergent laboratory abnormalities, defined as values that increase by at least one toxicity grade from baseline at any time postbaseline, up to the date of last dose of study drug plus 30 days will be summarized by cohort.

All laboratory abnormalities will be included in the listings of laboratory data.

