7.2.2.2. Summaries of Laboratory Abnormalities

Laboratory data that are categorical will be summarized using the number and percentage of subjects in the study with the given response at baseline and each scheduled postbaseline visit.

The following summaries (number and percentage of subjects) for treatment-emergent laboratory abnormalities will be provided by lab test and treatment group; subjects will be categorized according to the most severe postbaseline abnormality grade for a given lab test:

- Graded laboratory abnormalities
- Grade 3 or 4 laboratory abnormalities

For all summaries of laboratory abnormalities, the denominator is the number of subjects with nonmissing postbaseline values up to 30 days after last dosing date.

A by-subject listing of treatment-emergent Grade 3 or 4 laboratory abnormalities will be provided by unique subject ID number and visit in chronological order. This listing will include all test results that were collected throughout the study for the lab test of interest, with all applicable severity grades or abnormal flags displayed.

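### ALT/AST rebounds that stay at or below the baseline grade drop out of the treatment-emergent laboratory tables, even above 5x nadir; a nadir-based count would close the gap cheaply

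*SAP*

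**What the plan says.** SAP 7.2.2.1 gives the definition: "Treatment-emergent laboratory abnormalities are defined as values that increase at least 1 toxicity grade from baseline at any postbaseline time point", with a window that ends 30 days after the last dose. Protocol 8.5.3 agrees: "values that increase by at least one toxicity grade from baseline at any time postbaseline". Baseline is fixed before treatment (SAP 7.2.1): "A baseline laboratory value will be defined as the last measurement obtained on or prior to the date/time of first dose of study drug".

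SAP 7.2.2.2 restricts both summary tables to abnormalities that meet this definition; within them, "subjects will be categorized according to the most severe postbaseline abnormality grade for a given lab test". The accompanying listing covers treatment-emergent Grade 3 or 4 abnormalities only.

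Three other provisions bear on the point:

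- **Entry.** Protocol 4.3, criterion 10, excludes "ALT >10 x upper limit of normal (ULN") at screening and sets the same limit for AST. Entry at Grade 1, 2 or 3 is therefore allowed.
- **Expected course.** ALT normalisation is a secondary endpoint (Protocol 8.1.3, SAP 6.2.1).
- **Site stopping rule.** One criterion of Protocol 3.3.1 looks back to the lowest value as well as to Day 1: "Elevation of ALT and/or AST above the upper limit of normal (ULN) and $> 5x$ Day 1 or nadir", with confirmation by repeat test.

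**The concern.** The tables measure a rise from where the subject started, while treatment is expected to move that starting point down. For a subject who enters with raised enzymes, normalises and then rebounds, the relevant comparison is with the on-treatment low. The stopping rule makes that comparison; the laboratory tables do not. The tables are therefore least sensitive to hepatic flares in the subjects who enter with the highest transaminases.

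Safety and tolerability is a primary objective. The protocol also relies on ALT elsewhere: subjects positive for HBV core antibody may enter, and Protocol 6.7.9 makes their HBV DNA test depend on ALT rising above ULN or above the Day 1 value. A report could show no treatment-emergent ALT or AST abnormality although a value had exceeded five times nadir.

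**Working it through.** The plan states no figure on this point, so there is none to reproduce. The check follows from the definitions.

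**Inputs.** Grades from Protocol Appendix 3, in multiples of ULN: Grade 1 is 1.25 to 2.5, Grade 2 is above 2.5 to 5, Grade 3 is above 5 to 10, Grade 4 is above 10. Anything lower is Grade 0. Let B be the baseline value, N the on-treatment nadir and F the later value, all in x ULN.

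- Treatment-emergent if grade(F) > grade(B).
- Nadir branch of the stopping rule exceeded if F > 1 and F > 5N.

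**Uncounted range.** Let U be the top of the baseline band (2.5, 5 or 10). A rebound exceeds the nadir branch but is not treatment-emergent when 5N < F ≤ U. This is possible only if N < U/5, that is 0.5, 1.0 or 2.0 x ULN for baseline Grades 1, 2 and 3. The documents give no nadirs, so the values below are assumptions. Lower ends mean just above the figure.

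| Baseline grade | N = 0.3 | N = 0.5 | N = 1.0 |
|---|---|---|---|
| 1 | 1.5 to 2.5 | none | none |
| 2 | 1.5 to 5 | 2.5 to 5 | none |
| 3 | 1.5 to 10 | 2.5 to 10 | 5 to 10 |

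**Cases.**

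| B | N | F | F/N | Baseline to F | Treatment-emergent? | Grades above nadir |
|---|---|---|---|---|---|---|
| 6 | 0.5 | 8 | 16 | G3 to G3 | no | 3 |
| 8 | 0.6 | 9 | 15 | G3 to G3 | no | 3 |
| 4 | 0.5 | 3 | 6 | G2 to G2 | no | 2 |
| 2 | 0.4 | 2.3 | 5.75 | G1 to G1 | no | 1 |
| 8 | 0.6 | 10.5 | 17.5 | G3 to G4 | yes | 4 |
| 4 | 0.5 | 5.2 | 10.4 | G2 to G3 | yes | 3 |
| 2 | 0.4 | 2.6 | 6.5 | G1 to G2 | yes | 2 |

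The last three rows show that a rebound above the baseline grade is counted.

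**Other ALT/AST criteria in Protocol 3.3.1.** The upper limit of each of the bands for Grades 1 to 3 is twice its lower limit, so a value more than three times Day 1 always leaves the band: 3 × 1.25 = 3.75 > 2.5; 3 × 2.5 = 7.5 > 5; 3 × 5 = 15 > 10. A baseline between 1 and 1.25 x ULN (Grade 0) goes above 3, which is Grade 2. The criterion "Abnormal elevation of ALT $> 3 x$ Day 1 and total bilirubin $> 2 x$ ULN" and the five-times-Day-1 branch are therefore always treatment-emergent on ALT alone. A value above 15 x ULN is Grade 4, above any baseline up to 10 x ULN. A grid search over baselines from just above 1 to 10 x ULN found no misses. Only the nadir branch can be missed.

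**Other outputs, for the 6 / 0.5 / 8 case.**

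- *On drug and confirmed.* Protocol 3.3.1 requires a stop, Protocol 7.1.3 then requires an adverse event record, and the event enters the discontinuation table (SAP 7.1.6) and the primary safety endpoint (Protocol 8.1.2). Captured.
- *At the posttreatment Week 4 draw.* No drug is left to stop, so a rise without symptoms or intervention creates no automatic adverse event.
- *Visit summaries (SAP 7.2.1).* The change from baseline is 8 − 6 = 2 x ULN, which adds 2/50 = 0.04 x ULN to a mean of 50. The visit maximum may show the value, but not that it followed normalisation.
- *ALT normalisation by visit (SAP 6.2.2).* The subject counts as not normalised at that visit. That does not separate a rebound from an enzyme that never fell, and AST is not covered.
- *Full laboratory listing (SAP 7.2).* The value is flagged, but nothing is counted.

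**The case against.** The strongest reply is that the serious version of this event is already reported. A confirmed on-treatment flare stops drug, becomes an adverse event and feeds the primary safety endpoint. An unconfirmed rise does not meet the stopping criterion, since confirmation is part of it. The adverse event route may also be wider than the automatic triggers: Protocol 7.1.3 leaves out abnormalities that lack clinical significance, and Protocol 7.1.1 implies that a clinically significant one arising after consent can qualify. Adverse events are collected for 30 days after the last dose. Every graded or out-of-range value is flagged in a listing. Protocol and SAP agree on the definition, and nothing requires a descriptive table to use the same reference as a stopping rule.

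Most of this stands. There is no contradiction or error, and the gap is smaller than the definition alone suggests. What remains is that, for flares not recorded as adverse events, no planned output counts them; a reader would have to find them value by value in the listings. The SAP already adds this kind of count elsewhere: SAP 7.2.1 tallies hemoglobin below 10 or 8.5 g/dL at any postbaseline visit, whatever the baseline grade.

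**Conclusion.** This is a worthwhile, low-cost improvement to hepatic safety reporting. An ALT or AST rebound after normalisation that stays at or below the baseline grade is left out of the treatment-emergent tables and the Grade 3 or 4 listing, even above 5x nadir. The cases that no output counts are mainly flares after the last dose to day +30, unconfirmed rises, and others not recorded as adverse events.

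Two stronger readings are tempting. A reader might infer that flares in subjects who enter with raised enzymes are generally uncounted; they are counted whenever they exceed the baseline grade. A reader might also infer that a subject stopped under Protocol 3.3.1 could vanish from the safety results; the adverse event requirement in Protocol 7.1.3 prevents that.

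Frequency cannot be computed, because the documents give no baseline ALT/AST distribution and no flare rate. One subject would be 1/50 = 2% of Cohort 1 or 1/30 = 3.3% of Cohort 2; that is scale, not an estimate. The ranges rest on the assumed nadirs. The finding that only the nadir branch is missed assumes a baseline above ULN and no higher than 10 x ULN; the entry limit applies at screening, so a higher Day 1 value is possible and lies outside the check.

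**What to change.** Keep the definition in SAP 7.2.2.1. Add to SAP 7.2.2.2, for ALT and AST separately and by treatment group:

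- the number and percentage of subjects whose value, through 30 days after the last dose, rises at least one grade above their lowest earlier grade since first dose;
- within that count, a flag for values above ULN and above five times Day 1 or nadir, whether or not confirmed and whether or not the subject was still on drug;
- a by-subject listing of these subjects with baseline, nadir, peak, dates and last dose date.

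Separate counts for the other ALT criteria of Protocol 3.3.1 are unnecessary, because the baseline rule already captures them within the range checked. No clinical rule changes.

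The cost is SAP wording, one table and one listing from data already collected. The downside is that some minor Grade 0 to Grade 1 rises will be shown; the flag separates them from the larger rebounds.
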